## 10. ANALYSIS OF SAFETY DATA

The analysis of safety and tolerance will be performed on the SAF .

The safety analysis will be based on the reported AEs and other safety information (clinical laboratory evaluations, vital signs and 12-lead ECG, etc.).

For safety variables, 3 observation periods are defined:

- The pre-treatment period is defined as the time from signing the screening ICF to before the first dose of study drug.
- The on-treatment period is defined as the time from first dose of study drug to the last dose of study drug plus 100 days or until the start of new systemic therapy for treatment of the patient's tumor (whichever is earlier).
- The post-treatment period is defined as the time starting 1 day after the end of on-treatment period.

### 10.1. Adverse Events

All AEs reported in this study will be coded using the Medical Dictionary for Regulatory Activities (MedDRA®) and graded using the current NCI-CTCAE.

Treatment-emergent adverse events are defined as AEs that develop or worsen during the on-treatment period and any treatment-related SAEs that occur during the post-treatment period.

All AEs reported in this study will be coded using Medical Dictionary for Regulatory Activities (MedDRA®).

Summaries of TEAEs will include but not limited to:

- Overview of TEAEs
- Treatment-related TEAEs and serious TEAEs by SOC and PT
- TEAEs by SOC and PT
- TEAEs by all grades and  $\geq$  grade 3, presented by SOC and PT
- Treatment-related TEAEs, presented by SOC and PT
- Treatment-emergent AESIs, presented by SOC and PT
- TEAEs leading to permanent treatment discontinuation, presented by SOC and PT
- TEAEs leading to death, presented by SOC and PT
- Serious TEAEs, presented by SOC and PT

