6.4.1. Adverse Events

AEs should be monitored and captured in the eCRF from the time that the ICF is signed through 100 days after the last dose of study drug (both vidutolimod and cemiplimab) or until an alternative anticancer treatment is initiated, whichever occurs first. Subjects who discontinue vidutolimod but remain on treatment with cemiplimab will continue to have AEs collected according to this schedule until 100 days after the last dose of study treatment. After 100 days post-treatment, only treatment-related SAEs will be recorded on the eCRF.

All AEs that started or worsened in severity on or after the date that study drug was first administered (W1D1) will be considered treatment-emergent adverse events (TEAEs). AEs that worsened (i.e. increase to higher severity/grade) should be recorded as new AEs. Ongoing AEs with a decrease in severity/grade do not need to be captured as new AEs. TEAEs will be graded according to CTCAE v5.0 and coded using the Medical Dictionary for Regulatory Activities (MedDRA). ISRs will be graded according to [Table 4](#).

AEs that are consistent with the mechanism of PD-1/PD-L1 blockade, or immune-mediated AEs for which other etiologies have been ruled out (e.g. infection or tumor progression), should be diagnosed and treated according to available guidelines (i.e. [Brahmer, 2018](#)). Immune-mediated AEs may include events with an alternate etiology that were exacerbated by the induction of autoimmunity. Information supporting the assessment will be collected on the eCRF.

A full description of AE collection and reporting procedures during this study is in Section [7.3](#).

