7.3. Procedures for Recording and Reporting Adverse Events

7.3.1. Individual Case Safety Reporting (ICSR)

All events (serious and non-serious) must be reported with investigator's assessment of the event's seriousness, severity, and causality to the (when applicable, blinded) study drug. For SAEs and AESIs, a detailed narrative summarizing the course of the event, including its evaluation, treatment, and outcome should be provided on the AE CRF. Specific or estimated dates of event onset, treatment, and resolution should be included, when available. Medical history, concomitant medications, and laboratory data that are relevant to the event should also be summarized in the narrative. For fatal events, the narrative should state whether an autopsy was or will be performed

and include the results if available. Information not available at the time of the initial report must be documented in a follow-up report. Source documents (including hospital or medical records, diagnostic reports, etc.) will be summarized in the narrative on the AE CRF and retained at the study center and available upon request.

Urgent safety queries must be followed up and addressed promptly. Follow-up information and response to non-urgent safety queries should be combined for reporting to provide the most complete data possible within each follow-up.

Adverse events will be recorded from the time of informed consent until 100 days after the last dose of study drug (both vidutolimod and cemiplimab) or until an alternative anticancer treatment is initiated, whichever occurs first. AEs starting more than 100 days after the last dose of study drug should not be recorded on the AE eCRF unless they are considered to be related to study treatment. The date, time of onset, resolution, determination of seriousness, severity, action taken, outcome and relationship to vidutolimod and cemiplimab will be recorded for all AEs.

All AEs and SAEs experienced by a subject will be recorded on the appropriate eCRF. In addition, for all SAEs a paper SAE Report Form will be completed and submitted within 24 hours of awareness.

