7.3.2. Reporting Serious Adverse Events

All SAEs and associated source documents must be reported in written or typed English via completion of the eCRF AE page and accompanying paper SAE Report Form (following the same reporting process outlined in Section 7.3) within 24 hours of first knowledge of the event regardless of relationship to the study procedures or individual study drugs. The paper SAE Report form should be used to record pertinent information, regarding the SAE. The Investigator is requested to supply as much detailed information as possible regarding the event at the time of the initial report.

SAEs will be collected from completion of the ICF until 100 days after the last dose of any study allowed drug treatment. SAEs starting more than 100 days after the last dose of study drug should not be recorded on the eCRF unless they are considered to be related to study treatment.

If at any time after the subject has completed participation in the study, the Investigator or study staff becomes aware of an SAE during the study reporting period that they believe is possibly, probably, or definitely related to either study drug (see Section 7.2.2), then the event and any known details must be reported promptly to the Sponsor or its representatives. The following reporting instructions must be followed.

At minimum, the Investigator will be asked to provide the following information:

- For the initial SAE notification, the Investigator must provide, at a minimum, basic information such as the protocol number, subject's year of birth or age at onset, subject identification number, period of study drug intake, event term, nature of the event, detailed description of the clinical course of the event, seriousness criteria, causality of the event to vidutolimod and cemiplimab separately, and severity.

- In addition, the initial SAE information entered on the eCRF and paper SAE Report Form should include all pertinent known information about the SAE and the affected subject, such as the following: subject sex; description of the AE including reason for assessment as serious, and individual study drug information including doses, dates of dosing, and action taken with individual study drugs.

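### The protocol gives two rules for recording related non-serious AEs after day 100, and SAP 10.1 leaves any that are recorded out of the TEAE and AESI tables

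*SAP*

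**What the plan says.** **Recording in the protocol.** Section 6.4.1 collects AEs from consent to 100 days after last dose or to the start of another anticancer treatment, whichever is earlier. It then says: "After 100 days post-treatment, only treatment-related SAEs will be recorded on the eCRF". Table 1 footnote j gives the same window and afterwards continues only SAEs related to study product. Section 7.3.1 has the same window but a different rule beyond it: "AEs starting more than 100 days after the last dose of study drug should not be recorded on the AE eCRF unless they are considered" related to study treatment. That exception has no seriousness condition.

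For SAEs, Section 7.3.2 says: "SAEs will be collected from completion of the ICF until 100 days after the last dose of any study allowed drug treatment". It has no stop at new anticancer treatment, and after day 100 it keeps related SAEs.

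**TEAE definition in the protocol.** Section 6.4.1 says: "All AEs that started or worsened in severity on or after the date that study drug was first administered (W1D1) will be considered" treatment-emergent. The sentence has no end date.

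**Analysis in the SAP.** SAP Section 10 ends the on-treatment period at the "last dose of study drug plus 100 days or until the start of new systemic therapy", whichever is earlier. SAP 10.1 builds on that period: "Treatment-emergent adverse events are defined as AEs that develop or worsen during the on-treatment period and any treatment-related SAEs that occur during the post-treatment period". Every AE summary it names is restricted to treatment-emergent events, including the AESI table.

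**Related text.** Protocol 7.3.4 defines AESIs as serious or non-serious and includes immune-mediated AEs of Grade 3 or higher. Protocol 6.1.6 and 8.4.8 collect the medications used to treat study-related AEs that occur more than 100 days after last dose. SAP 9.2 counts those medications as concomitant. None of these three sections requires the AE to be serious.

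**The concern.** Two sites reading different sections of the same protocol would treat the same late event differently. One would record a related, non-serious AE on day 120; the other would not. If the event is recorded, the SAP drops it from the summary tables because it is not serious.

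Safety and tolerability is a secondary objective, and the protocol singles out immune-mediated AEs of Grade 3 or higher for expedited reporting whether serious or not. Late, related toxicity is what the day-100 exception in 7.3.1 exists to catch. At stake is whether the TEAE and AESI tables describe that toxicity completely, and whether the data behind them were gathered under one rule.

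**Working it through.** The documents state no figure on this point, so the check is a comparison of rules. The day numbers below are illustrative and count from last dose.

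**Case 1: related, non-serious Grade 3 immune-mediated AE, onset day 120, no new therapy**

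| Source | Result |
|---|---|
| Protocol 6.4.1, TEAE sentence | Treatment-emergent |
| Protocol 6.4.1, recording sentence | Not recorded |
| Table 1 footnote j | Not followed further |
| Protocol 7.3.1 | Recorded on the AE eCRF |
| Protocol 7.3.4 | Meets the AESI definition |
| Protocol 6.1.6 and 8.4.8 | Its treatment medication is collected |
| SAP 9.2 | That medication is tabulated as concomitant |
| SAP 10 and 10.1 | Post-treatment and not an SAE, so not a TEAE; absent from the TEAE, related-TEAE, Grade 3 or higher and AESI tables |

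The protocol contradicts itself on recording. If the event is recorded, the SAP can show the drug given for it but not the event.

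**Case 2: the same event, but serious.** 6.4.1, footnote j, 7.3.1 and 7.3.2 all keep it, and SAP 10.1 counts it. The conflict is confined to non-serious related events.

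**Case 3: related, non-serious AE, onset day 50, new anticancer therapy on day 35.** Routine AE collection under 6.4.1 and 7.3.1 closed on day 35. The 7.3.1 exception begins only after day 100. Here the SAP drops nothing that the protocol routinely collects.

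**Case 4: unrelated SAE, onset day 50, new anticancer therapy on day 35.** 7.3.2 collects it, because its window runs to day 100 with no new-therapy stop. The AE windows in 6.4.1 and 7.3.1 closed on day 35. This is a second conflict in collection. The stop is also worded differently: the protocol refers to any alternative anticancer treatment, while the SAP period runs "until the start of new systemic therapy for treatment of the" tumor, that is, systemic treatment only.

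**Scale.** Planned sizes are about 25 per cohort and 9 × 25 = 225 in all (protocol 8.1, SAP 2.2). One omitted subject changes a cohort percentage by 1/25 = 4.0 points and the overall percentage by 1/225 = 0.44 points.

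The documents give no rate p of subjects with a late, related, non-serious AE. Over an assumed range, the chance that a cohort of 25 has at least one is 1 − (1 − p)^25, and the expected number among 225 is 225p:

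| Assumed p | At least one in 25 | Expected in 225 |
|---|---|---|
| 0.5% | 11.8% | 1.1 |
| 1% | 22.2% | 2.3 |
| 2% | 39.7% | 4.5 |
| 5% | 72.3% | 11.3 |

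These rows show scale only. They do not estimate the loss in this trial.

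**The case against.** The best defense is that the SAP follows the protocol. Its post-treatment rule matches the recording sentence in 6.4.1 and footnote j, and 7.3.1 is the outlier. That is correct, and it means the protocol must be reconciled first. It does not settle the matter while 7.3.1 remains in force and the medication rules in 6.1.6, 8.4.8 and SAP 9.2 presuppose late related AEs.

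The second defense is that nothing need be lost altogether. Protocol 8.7.1 plans a by-subject AE listing not restricted to TEAEs. SAP 10.1 says its list of summaries is not exhaustive. AESIs reach the sponsor under 7.3.4, and 7.3.6 has investigators notify related AEs learned of after discharge. This stands: the effect is confined to the summary tables and to uneven recording. It does not make those tables complete.

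A reader might also infer four stronger points, which the documents do not support:

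- **The SAP discards AEs that start after new therapy and before day 100.** Routine collection closes at new therapy, so the SAP has no routinely collected non-serious events there to discard. Extending that collection is a debatable design choice, because attribution becomes confounded.
- **The enrollment-hold rule is affected.** Protocol 6.4 bases it on cumulative AEs and the observed rate of Grade 3 or higher immune-mediated AEs, not on SAP-defined TEAEs.
- **SAP 1.4 is wrong to report no modifications.** That section concerns the protocol's statistical section; the TEAE definition sits in 6.4.1.
- **Rates are biased between cohorts.** The documents give neither times to new therapy nor rates of late events by cohort.

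**Conclusion.** The plan is inconsistent as written and should be corrected. Protocol 6.4.1 and footnote j conflict with 7.3.1 on related, non-serious AEs after day 100. If 7.3.1 governs, SAP 10.1 keeps recorded events of that kind out of every TEAE and AESI summary it names, although the 6.4.1 TEAE sentence would include them. SAE collection in 7.3.2 also lacks the new-therapy stop that applies to AEs.

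The reach is limited. Related serious late events still count, and a listing can still show the rest. A claim that delayed toxicity will be under-reported by a known amount would go too far: the omission depends on such events being recorded, and their frequency cannot be derived from the documents. What is certain is the direction, since against the 6.4.1 definition the SAP can only lower the counts, and the 4-point step per omitted subject in a cohort of 25.

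**What to change.** 1. **Protocol.** Reconcile 6.4.1 and Table 1 footnote j with 7.3.1, so that one rule governs related AEs after day 100. State whether the TEAE definition in 6.4.1 has an end date.
2. **SAP 10.1.** Align it with that rule. If 7.3.1 stands, replace "any treatment-related SAEs that occur during the post-treatment period" with wording that covers treatment-related AEs in that period whether serious or not. Alternatively, keep the definition and tabulate those events separately, with late AESIs and immune-mediated AEs shown. If 6.4.1 stands instead, the post-treatment part of SAP 10.1 can stay, and 7.3.1 and the late-medication rules should be brought into line.
3. **New-therapy stop.** State whether it applies to SAEs, so that 7.3.2 agrees with 6.4.1 and 7.3.1, and use one term for it in protocol and SAP.
4. **Flag.** Mark events that start after new anticancer therapy, so that readers can set them apart.

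The cost is a protocol clarification, a wording change in the SAP and perhaps a few more eCRF entries. The 100-day contact already asks about new AEs and other cancer treatments. The downside is a small number of late events with confounded attribution, which the flag handles.

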### 10.2. Laboratory Parameters

The clinical laboratory data consists of serum chemistry, hematology, urinalysis.

Clinical laboratory analytes will be converted to standard international (SI) units and grouped by function in summary tables for each chart on the SAF. Clinical laboratory values and change from baseline in clinical laboratory values to all scheduled assessment times will be summarized with

descriptive statistics. Summary tables for worst laboratory values during on-treatment period with CTCAE all grade and grade  $\geq 3$  will be generated. Shift tables from baseline to worst post-treatment NCI CTCAE grade during on-treatment period will be generated.

### **10.3. Vital Signs**

The following vital signs parameters will be recorded and summarized:

- Respiratory rate (bpm)
- Pulse rate (bpm)
- Sitting systolic and diastolic blood pressures (mmHg)
- Body temperature ( $^{\circ}\text{C}$ )

Vital sign parameters will be summarized by baseline and change from baseline to each scheduled assessment time with descriptive statistics for each cohort.

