- i. Vital signs include measurement of blood pressure (systolic and diastolic blood pressure), respiratory rate, heart rate, and body temperature. Blood pressure and heart rate should be taken in the seated position following ≥ 3 minutes of rest. For the first 6 vidutolimod dosing visits (W1D1 to W6D1), vital signs must be collected prior to the vidutolimod injection (± 10 minutes) and at 30-minute (± 15 minutes) intervals for 4 hours after vidutolimod injection. Starting at W7D1, observation periods may be reduced to a minimum of 1 hour following vidutolimod injection at the Investigator's discretion based on the AE profile of the individual subject. When vital signs are scheduled at the same time as collection of a blood sample, the vital sign measurements should be obtained before the scheduled phlebotomy. If a study visit occurs where only cemiplimab is administered, vital signs must be collected before the start of cemiplimab infusion.

NOTE: Oxygen saturation is not a required parameter to be collected. Sites are to capture oxygen saturation every time an AE of hypoxia or CRS is reported for a subject.

- j. AEs will be assessed from time of consent through 100 days after the last dose of study treatment or until an alternative anticancer treatment is initiated, whichever occurs first. Subjects who discontinue vidutolimod but remain on treatment with cemiplimab will continue to have AEs collected according to this schedule until 100 days after the last dose of cemiplimab or until an alternative anticancer treatment is initiated, whichever occurs first. Any SAEs related to IP will continue to be assessed.
- k. Concomitant medications will be assessed continually from 30 days before the first dose of study treatment through 100 days after the last dose of study treatment or until an alternative anticancer treatment is initiated, whichever occurs first. Treatment medications for study-related AEs that occur through 100 days after the last dose of study treatment will be collected during the 100DFU period.
- l. 12-lead ECGs will be obtained at Screening, before the W1D1, W3D1, and W7D1 vidutolimod injections, and at EOT. ECG parameters will include heart rate and PR interval, QRS, QT, and QTc intervals. ECGs will be performed after the subject has been resting in supine or semi-supine position for at least 5 minutes. When an ECG is scheduled at the same time as a blood sampling, the ECG reading should be obtained before the scheduled blood sampling.

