1.3.1.3. Previous Clinical Studies with Vidutolimod

Several clinical studies evaluating the addition of a TLR9 agonist to immune checkpoint inhibition have been conducted, including vidutolimod in combination with pembrolizumab in subjects with PD-1 refractory melanoma (Study CMP-001-001) and in treatment-naïve Stage III melanoma (Study HCC 17-169), as described below.

The clinical benefit of vidutolimod IT in combination with intravenous (IV) pembrolizumab has been demonstrated in patients with melanoma refractory to PD-1 blockade in the ongoing Study CMP-001-001 (subjects treated with pembrolizumab according to the KEYTRUDA® (pembrolizumab) United States Prescribing Information (USPI) ([KEYTRUDA, 2020](#)) in combination with vidutolimod 10 mg IT every week for 7 weeks then every 3 weeks (Q3W) thereafter, the objective response rate (ORR) was 27.6% (27/98; 95% CI 19.0%, 37.6%), including subjects with responses after initial progressive disease (PD), and the best ORR by Response Evaluation Criteria in Solid Tumors Version 1.1 (RECIST v1.1) was 23.5% (23/98; 95% CI 15.5%, 33.1%), including 7 complete responses (CR) and 16 partial responses (PR). This ORR is substantially higher than the 7.7% response rate observed in the 6 of 78 subjects who received treatment beyond progression with pembrolizumab in the Keynote-002 study ([Ahmed, 2020](#)). The clinical benefit of this combination treatment includes durable CRs and PRs in injected and noninjected target lesions and non-target lesions of the skin, lymph nodes, and viscera. The Kaplan-Meier estimate for median duration of response (DOR) for both RECIST v1.1 responders and RECIST v1.1 responders plus post-PD responders was 19.9 months (95% CI 6, 19.9). Most treatment-related adverse events (AEs) were Grade 1 or 2 and included flu-like symptoms, including chills, fever, fatigue, nausea, vomiting, and headache, and injection site pain. The most common treatment-related Grade 3 or 4 AEs were hypotension (6.3%) and hypertension (5.0%). No Grade 5 treatment-related AEs were reported. Additional information is provided in the Vidutolimod Investigator’s Brochure (IB).

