4.1.1.5. Management of Adverse Events Associated with Vidutolimod

[figure not shown]
Based on observations in earlier studies, vidutolimod has been associated with AEs such as injection site reactions (see Section 4.1.1.5.1), hypotension, CRS, and flu-like symptoms. Flu-like symptoms could include fever, nausea, vomiting, chills, rigors, and/or hypotension. Additional symptoms may occur, such as headache, tachycardia, rash, and hypoxia. Symptoms should be expected within 1 to 4 hours following the injection but may also occur outside this window.

Sites are to capture oxygen saturation every time an AE of hypoxia or cytokine release syndrome (CRS) is reported for a subject.

Required prophylaxis is designed to prevent or minimize the severity of these symptoms (see Section 4.1.1.1).

The following algorithm (Figure 2) is provided as guidance for prophylaxis and treatment of AEs associated with vidutolimod.

Figure 2: Prophylaxis and Treatment for Adverse Events Associated with Vidutolimod

Abbreviations: AE = adverse event; IV = intravenous(ly); NSAID = non-steroidal anti-inflammatory drug; PO = orally.

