#### **4. GENERAL STATISTICAL ANALYSIS CONSIDERATIONS**

Unless otherwise stated, the following conventions will be applied when presenting summary level statistics for data.

For continuous variables, descriptive statistics will include the following information: the number of patients reflected in the calculation (n), mean, standard deviation, Q1, median, Q3, minimum, and maximum.

For categorical or ordinal data, frequencies and percentages will be displayed for each category.

All analyses will be done using SAS Version 9.4 or above.

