### 11.1. Definition of Baseline for Efficacy/Safety Variables

Unless otherwise specified, the baseline assessment for all measurements will be the latest available valid measurement taken prior to the administration of investigational product.

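### SAP 10.3 gives no per-subject worst post-injection vital sign, no count of subjects affected and no comparison with the same-visit pre-injection reading

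*SAP*

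**What the plan says.** **Collection.** Footnote i of the protocol's Schedule of Assessments requires vital signs before each injection from W1D1 to W6D1 and then "at 30-minute (± 15 minutes) intervals for 4 hours after vidutolimod injection". From W7D1 the investigator may shorten observation to as little as 1 hour, depending on the subject's AE profile. Protocol 4.1.1.5 explains the timing: "Symptoms should be expected within 1 to 4 hours following the injection but may also occur outside this window". Protocol 1.4 adds that fever and hypotension, among other events, typically follow the second and later doses and generally settle within a few hours.

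**Analysis.** SAP 10.3 plans one summary: "Vital sign parameters will be summarized by baseline and change from baseline to each scheduled assessment time with descriptive statistics for each cohort". SAP 4 defines descriptive statistics for continuous variables as n plus "mean, standard deviation, Q1, median, Q3, minimum, and maximum". SAP 11.1 takes as baseline "the latest available valid measurement taken prior to the administration of investigational product". SAP 11.4 summarises scheduled assessments by nominal visit number and does not mention the 30-minute readings within a visit.

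**Related provisions.** Protocol 8.7.3 plans the same kind of summary by cohort and overall, a by-subject listing of all vital signs, and AE reporting of clinically significant findings. SAP 10.3 repeats neither the overall summary nor the listing, although SAP 1.4 declares no modifications. For laboratory data SAP 10.2 plans "Summary tables for worst laboratory values during on-treatment period" and shift tables. SAP 10.4 plans shift tables for ECG status.

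**The concern.** The serial readings are meant to describe an acute effect that is brief, varies in timing between subjects, and can go in either direction. In the prior melanoma study (protocol 1.3.1.3) the two most common related Grade 3 or 4 events were hypotension and hypertension. The natural questions are per subject and per injection: how far did this subject's blood pressure fall or rise after this injection, and in how many subjects was the change marked?

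A summary by scheduled time against one early baseline answers neither question:

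- The same subject's worst reading falls at different times at different visits, and no table brings those readings together.
- A post-injection value at W6D1 is compared with one taken about 5 weeks earlier, although a reading from just before that injection exists. Drift over those weeks is mixed with the acute effect.
- From W7D1, readings after 1 hour come only from subjects whose observation was not shortened. That choice depends on their AE profile, so the later summaries describe a selected group.

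At stake is how well the measured haemodynamic effect is described, as a complement to what investigators choose to report as AEs.

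**Working it through.** The documents give no figure for the vital-sign summary, so there is none to reproduce. The check is what the planned table can and cannot show.

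**Inputs from the documents:** about 25 subjects per cohort and 225 in all (protocol 8.1); six visits with 8 post-injection readings each (4 hours at 30 minutes); prior Grade 3 or 4 rates of 6.3% for hypotension and 5.0% for hypertension (protocol 1.3.1.3).

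**Assumptions (not in the documents):** SD of change in systolic pressure 10 to 15 mmHg (12 to 20 in step 2); excursions of 30 to 50 mmHg; a table laid out by visit and reading time, which SAP 11.4 does not specify.

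1. *Number of cells.* 6 × 8 = 48 post-injection summaries per parameter per cohort.

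2. *The mean.* One fall of 40 mmHg among 25 subjects shifts that cell's mean by 40/25 = 1.6 mmHg. One fall and one rise of 40 in the same cell shift it by 0. Suppose 6.3% of subjects each have one episode lasting k = 1 to 4 of the 48 readings. The average shift per cell is then 0.063 × fall × k/48, which runs from 0.063 × 30 × 1/48 = 0.04 to 0.063 × 50 × 4/48 = 0.26 mmHg. The standard error of a cell mean is 12/√25 = 2.4 to 20/√25 = 4.0 mmHg. The mean is uninformative here.

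3. *The minimum and maximum in one cell.* Simulating 25 normal changes with SD 12 and adding one -40 and one +40 excursion moves the average minimum from -23.5 to -40.7, the maximum from +23.6 to +40.7 and the SD from 11.9 to 16.5. Within a single cell, these statistics do show the excursions.

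4. *The minimum over all cells.* A reader scans 48 cells. Simulating 25 subjects × 48 readings with no episode at all (within-subject correlation 0 to 0.7), the lowest value in the cohort's tables averages:

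| SD | Average lowest change | Chance it is -40 mmHg or below |
|---|---|---|
| 10 | -29 to -33 | 2% to 4% |
| 12 | -35 to -40 | 19% to 40% |
| 15 | -44 to -50 | 73% to 99% |

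   A minimum near -40 stands out if the SD is 10, is ambiguous at 12, and is expected at 15. In no case does it show whether one subject or several were affected, or whether two low cells belong to the same subject.

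5. *Reference value.* W6D1 is 5 weeks after W1D1. The same-visit pre-injection value is collected, but no planned change uses it.

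6. *Comparison within the SAP.* Laboratory data get worst on-treatment values and shift tables; ECG status gets shift tables. Vital signs get neither.

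**The case against.** A reader might infer that the plan shows only average change, so that falls and rises cancel and disappear. The documents do not support that. SAP 4 puts the SD, quartiles, minimum and maximum in the same table, and protocol 8.7.3 also names the minimum and maximum. Step 3 shows that they respond where the mean does not. Cancellation in the mean also needs opposite episodes in the same cell, which would be uncommon if episodes are scattered over 48 readings.

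A reader might also infer that this is the only analysis of acute hypotension, so that about 0.063 × 225 = 14 affected subjects would go uncounted. That does not hold either. The 6.3% is a rate of Grade 3 or 4 AEs, and SAP 10.1 tabulates TEAEs of Grade 3 or higher, related TEAEs and AEs of special interest. Under protocol 7.3.4 the last group includes Grade 3 or higher hypotension and Grade 2 or higher cytokine release syndrome, which covers hypotension responding to fluids beyond baseline prophylaxis. Clinically significant vital-sign findings must be reported as AEs, and protocol 8.7.3 provides a full listing.

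Three further points stand. The SAP's baseline wording does not say first administration, so the pre-W1D1 reading is an interpretation. The n required by SAP 4 would already show how many subjects remain at each summarised time. The study is descriptive and exploratory (SAP 1.2).

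This leaves the gap smaller, but does not close it. The AE route depends on the investigator judging a finding clinically significant in an open-label study. Falls managed within the prophylactic fluid regimen need not become an AE of special interest. A listing supplies the raw values but no summary.

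**Conclusion.** The point holds in limited form. The planned table shows the extreme at each summarised time, and the AE tables count reported events. No planned table gives a subject's worst post-injection value, the number of subjects with a marked measured change, or the change from the same-visit pre-injection reading. The SAP also does not say how the 30-minute readings within a visit are summarised.

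The size depends on assumed variability. With 48 readings and 25 subjects, the table-wide minimum averages about -30 to -50 mmHg by chance alone for SDs of 10 to 15, so it cannot replace a per-subject summary except at the low end of that range. The documents allow no estimate of how many measured episodes the AE tables would miss, and none is claimed. This is a worthwhile, inexpensive improvement to a safety summary. It does not affect the primary analysis and does not mean that acute toxicity would go unreported.

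**What to change.** In SAP 10.3:

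- For each injection visit, add the change from that visit's pre-injection value to the worst post-injection value: lowest and highest systolic pressure, highest pulse, highest temperature.
- Add the number and percent of subjects beyond prespecified thresholds at any visit, by cohort and overall. The sponsor should choose these as reporting thresholds; they are not treatment rules.
- State how the 30-minute readings are summarised and which value is the baseline. Restore the overall summary and the by-subject listing from protocol 8.7.3, or record their omission in SAP 1.4.
- From W7D1, show readings after 1 hour with the number still observed and interpret them accordingly, or limit by-time summaries to the first hour.

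One caution for the thresholds: counts over many readings also pick up noise. For a fall of 30 mmHg at SD 12, the chance per reading is Φ(-30/12) = 0.0062, and over 48 independent readings it is 1 - (1 - 0.0062)^48 = 26% of subjects. Requiring an absolute level as well as a change, or persistence over consecutive readings, would reduce this.

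The cost is SAP wording and one or two extra tables from data already collected. No new assessments are needed.
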